9.0 AEs AND SAEs

9.1 AEs

9.1.1 AE Definition

An AE is any untoward medical occurrence in a patient administered a pharmaceutical product and which does not necessarily have a causal relationship with the pharmaceutical product. An AE can, therefore, be any unfavorable and unintended sign, symptom, or disease temporally associated with the use of a medicinal product, whether or not related to the medicinal product. Any worsening of the patient's disease under study or other medical conditions will also be considered to be an AE, unless it is within the normal range of disease fluctuation for that patient.

Clinically meaningful (for a given patient) changes in physical examination findings and abnormal objective test findings (e.g., clinical laboratory tests) are also recorded as AEs. The criteria for determining whether an abnormal objective test finding should be reported as an AE are as follows:

1. Test result is associated with accompanying symptoms, and/or;
2. Test result requires additional diagnostic testing or medical/surgical intervention, and/or;
3. Test result leads to a change in study dosing or withdrawal from the study, significant additional concomitant drug treatment or other therapy, and/or;
4. Test result leads to any of the outcomes included in the definition of an SAE (Section 9.2).

Merely repeating a test, in the absence of any of the above conditions, does not meet condition number 2 above for reporting as an AE.

Any abnormal test result that is determined to be an error does not require reporting as an AE.

A treatment-emergent AE (TEAE) is defined as an AE that begins after the start of the double-masked study treatment or an event that begins before the start of the double-masked study treatment and worsens in intensity after starting double-masked study treatment.

9.1.2 Reporting of AEs

At each evaluation, the Investigator will determine whether any AEs have occurred. The patient will be questioned in a general way and no specific symptoms will be suggested. If any AEs have occurred, they will be recorded on the AE pages of the eCRF and in the patient's medical record. If known, the diagnosis will be recorded, in preference to the listing of individual signs and symptoms.

AE reporting begins when informed consent is obtained and ends at the conclusion of the study, unless an unresolved AE is still being followed.

The severity of the AE will be graded as follows:

Mild	The AE is easily tolerated and does not interfere with normal daily activities.
Moderate	The AE causes some interference with daily activities.
Severe	The AE causes all normal daily activities to be completely halted.

The relationship of each AE to the study drug will be determined by the Investigator using these explanations:

- **Related:** A reasonable possibility exists that the study drug caused the AE. A related AE can be further defined as follows:
 - Occurs within a reasonable temporal sequence to administration of study drug
 - Cannot be explained by concurrent disease or other drugs or chemicals
 - Improves or disappears on stopping or reducing study drug (de-challenge)
 - Reappears on repeated exposure to study drug (re-challenge)
 - Is an unusual event that is known to be associated with the drug or this class of compound, and cannot be explained by other therapy or the participant's physical condition
 - Unlikely to be attributed to concurrent disease or other drugs or a clinically reasonable response on withdrawal (de-challenge)
- **Not Related:** A reasonable possibility does not exist that the study drug caused the AE. A not related AE can be further defined as follows:
 - Occurs with a temporal relationship to administration of study drug which makes a causal relationship improbable
 - Other drugs, chemicals or underlying disease provide plausible explanations of causality
 - Is known to be associated with the participant's clinical condition, or with other medication taken by the participant

The Investigator will record each action taken and outcome for each AE according to the following:

Action taken

- None
- Treatment required
- Hospitalization
- Study drug interrupted

- Study drug discontinued
- Patient withdrawn
- Other (specify)

Outcome

- Recovered
- Recovered with sequelae
- Recovering
- Ongoing
- Death
- Lost to follow-up

Whether each AE is ocular or non-ocular will be determined by the Investigator for each AE and it will be recorded on the AE pages of the eCRF.

9.1.3 Follow-up of AEs

If any AEs are present when a patient completes the study, or if a patient is withdrawn from the study, the patient will be re-evaluated. At the Investigator's discretion, minor AEs can be re-evaluated via telephone and documented. If the AE is still not resolved, additional follow-up will be performed as appropriate. Every effort will be made by the Investigator or delegate to contact the patient until the AE is resolved or stabilized, or the medical monitor and Investigator agree that further follow-up is not necessary. The follow-up of AEs after post-dose assessments at Visits 6.5 or 10 will be documented in the patient's medical records.

9.2 SAEs

9.2.1 SAE Definition

An SAE is any untoward medical occurrence that at any dose:

- Results in death
- Is life-threatening
- Requires patient hospitalization or prolongation of existing hospitalization
- Results in persistent or significant disability/incapacity
- Is a congenital anomaly/birth defect

Medical and scientific judgment will be exercised in deciding whether expedited reporting is appropriate in other situations, such as important medical events that may not be immediately life-threatening or result in death or hospitalization but may jeopardize the patient or may require intervention to prevent one of the other outcomes listed in the

definition above. Events that require expedited reporting will also be considered to be SAEs.

9.2.1.1 Life-Threatening AEs

The term *life-threatening* in the definition of *serious* refers to an event in which the patient was at risk of death at the time of the event. It does not refer to an event which hypothetically might have caused death, if it were more severe.

9.2.1.2 Hospitalization

Hospitalization is defined as the patient being hospitalized overnight, or the patient's hospital stay being prolonged for at least an additional overnight stay. Pre-planned hospital stays or hospital stays for non-medical social reasons are not applicable. Twenty-three-hour hospitalizations for observation will be discussed with the medical monitor to determine whether they are appropriate for SAE reporting.

9.2.2 Reporting of SAEs

All SAEs occurring from the time of informed consent until Visit 6.5 (patients enrolled in the Primary Period only) or Visit 10 (all other patients) must be reported to the CRO safety personnel within 24 hours of the knowledge of the occurrence (this refers to any AE that meets any of the aforementioned serious criteria). All SAEs that the Investigator considers related to study drug occurring after post-dose assessments at Visits 6.5 or 10 must be reported to the CRO or the sponsor/designee.

To report the SAE, the site staff will complete the SAE form electronically in the electronic data capture (EDC) system for the study. When the form is completed, the CRO safety personnel will be notified electronically and will retrieve the form. If the event meets serious criteria and it is not possible to access the EDC system, site staff will send a completed paper SAE form to [REDACTED] within 24 hours of awareness. When the EDC system becomes available, the SAE information must be entered within 24 hours.

The Investigator must continue to follow-up with the patient until the SAE has subsided or until the condition becomes chronic in nature, stabilizes (in the case of persistent impairment), or the patient dies.

Within 24 hours of receipt of follow-up information, the Investigator must update the SAE form electronically in the EDC system for the study and submit any supporting

documentation (e.g., patient discharge summary or autopsy reports) to [REDACTED]. If it is not possible to access the EDC system, refer to the procedures outlined above for initial reporting of SAEs. Written confirmation that any serious, unexpected, and related AEs have been submitted to the IRB/IEC/REC must be forwarded to the sponsor and kept in the Investigator files.

9.2.3 Serious Unexpected Suspected Adverse Reactions

According to FDA CFR 312.32(a) and FDA Guidance “Safety Reporting Requirements for Investigational New Drugs (INDs) and BA/BE (Bioavailability/Bioequivalence) Studies” finalized December 2012, *suspected adverse reaction* means any AE for which there is a reasonable possibility that the medicinal product caused the AE. The phrase reasonable possibility means there is evidence to suggest a causal relationship between the AE and the medicinal product.

The following are examples of types of evidence that would suggest a causal relationship between the drug and the AE (i.e., *reasonable possibility*):

- A single occurrence of an event that is uncommon and known to be strongly associated with drug exposure (e.g., angioedema, hepatic injury, Stevens-Johnson syndrome)
- One or more occurrences of an event that is not commonly associated with drug exposure, but is otherwise uncommon in the population exposed to the drug (e.g., tendon rupture)

Suspected adverse reactions are the subset of all AEs for which there is a reasonable possibility that the drug caused the event. The Investigator will initially classify the relatedness of an AE, but the final classification is subject to the medical monitor’s determination unless revised by the sponsor, which has the ultimate responsibility for judging relatedness.

A suspected adverse reaction is considered *unexpected* if it is not listed in the Reference Safety Information in Section 6 of the K-161 Investigator’s Brochure or is not listed at the specificity or severity that has been described in the K-161 Investigator’s Brochure.

An AE or suspected adverse reaction is considered *serious* if, in the view of either the Investigator or sponsor, it results in any of the following outcomes: Death, a life-threatening AE, inpatient hospitalization or prolongation of existing hospitalization, a persistent or significant incapacity or substantial disruption of the ability to conduct normal life functions, or a congenital anomaly/birth defect (Section 9.2.1). Important medical events that may not result in death, be life-threatening, or require hospitalization may be considered serious when, based upon appropriate medical judgment, they may jeopardize the patient or patient and may require medical or surgical intervention to prevent one of the outcomes listed in this definition.

Any AE meeting the definitions of suspected adverse reaction, unexpected, and serious is considered a serious unexpected suspected adverse reaction (SUSAR). In accordance with the FDA Guidance “Safety Reporting Requirements for INDs and BA/BE Studies” finalized December 2012, the sponsor will unmask the study data for patients

experiencing SUSARs and only report those for patients who are on the active K-161 product. All such reports will be submitted to the Investigator(s), FDA, and IRB/IEC/REC in an expedited manner.

9.3 [REDACTED]

[REDACTED]

[REDACTED]

9.4 Patient Withdrawal and Drug Discontinuation

If a patient experiences an AE that leads to discontinuation of study drug treatment, the eCRF will identify the AE as the reason for drug discontinuation.

If a patient experiences an AE and withdraws informed consent and rejects the remaining scheduled visits, it is considered a patient withdrawal and the eCRF will identify the AE as the reason for withdrawal.

10.0 STATISTICAL METHODS AND DATA ANALYSIS

10.1 Sample Size Justification

The parameters to be needed for the calculation of sample size were estimated from the previous Phase 2 study (K-161-2.01US). In order to take intercurrent events (ICEs) into account, 4 different patient patterns are considered: (1) patients who were assigned to K-161 [REDACTED] and had an ICE, (2) patients who were assigned to K-161 [REDACTED] and did not have an ICE, (3) patients who were assigned to vehicle and had an ICE, and (4) patients who were assigned to vehicle and did not have an ICE.

Regarding EDS (VAS), a population mean in each pattern is assumed as follows:

Assigned Treatment	Intercurrent Event	
	Not Occurred	Occurred
K-161 [REDACTED]	(1) -10.0	(2) -3.6
Vehicle	(3) -3.6	(4) -3.6

A common variance, 431.2, and a common ICE occurrence rate, 8%, are assumed among the patterns. In order for EDS (VAS) to have at least 90% power when Holm's method is applied, i.e., in order to have 90% probability that EDS (VAS) is statistically significant when an alpha is set to 0.025 (two-sided), 310 patients/arm will be needed.

10.2 Targeted Estimand

The summary of the targeted estimand is as follows:

Treatment Condition

Treatment condition based on the assigned treatment group.

Population

DED patients based on the Inclusion and Exclusion criteria of the study.

Variable

Change from baseline to Day 85 in conjunctival sum fluorescein staining score and EDS (VAS) including measurements after intercurrent events (i.e., treatment policy strategy). Potential intercurrent events of the study are as follows:

- Discontinuation of the study treatment due to an adverse event
- Discontinuation of the study treatment due to lack of efficacy

Population-level Summary

Difference in means between the two treatment conditions.

10.3 Study Populations

The following analysis populations will be considered:

Full Analysis Set (FAS) in the 12-week Primary Period: will include all randomized patients who received at least 1 dose of study treatment. Patients will be analyzed according to their randomized treatment group, regardless of whether they adhere to their assigned treatment. The FAS will be used as the primary efficacy analyses.

Per Protocol Set (PPS) in the 12-week Primary Period: will include all randomized patients without any major protocol deviations and have valid baseline and Day 85 primary endpoint values. Major protocol deviations will be pre-specified prior to unmasking the study. PPS will be used to assess robustness of the primary analysis results.

Safety Population in the 12-week Primary Period: will include all randomized patients who have received at least 1 dose of study treatment.

FAS in the 52-week Overall Period: will include the randomized patients who are assigned into the 52-week Overall Period and received at least 1 dose of study treatment. Patients will be analyzed according to their randomized treatment group, regardless of whether they adhere to their assigned treatment.

Safety Population in the 52-week Overall Period: will include randomized patients for the 52-week Overall Period and who had at least 1 dose of study treatment.

10.4 Analysis of Efficacy Parameters

The primary efficacy endpoints are change from baseline to Day 85 in conjunctival sum fluorescein staining score on study eye and EDS (VAS), which are used regardless of whether or not the following ICEs occur: discontinuation of the study treatment due to an AE or lack of efficacy. Patients' measurements will be made even after occurrence of those ICEs. For each of the primary endpoints, the analysis of covariance with baseline value, sex and treatment as covariates is used in order to make a comparison between the treatment groups. Least squares means will be calculated for the comparison.

The data set to be used for the primary analyses is the FAS.

Missing values will be imputed using the pattern mixture model (PMM) with multiple imputation (MI). Patterns to be used for the PMM are, as feasible, determined in each treatment group by whether or not patients had an ICE, or the type of ICEs if patients had an ICE. For example, if patients who discontinued the study treatment due to an AE had missing values, their missing values will be imputed from the patients who had the same ICE, i.e., discontinuation of the study treatment due to an AE. If enough patients to develop an imputation model in each pattern do not exist, the control-based mean imputation proposed by Mehrotra ([Mehrotra 2017](#)) will be applied instead of the PMM with MI.

If the MI is applied, multiple parameter estimates will be combined using Rubin's rule ([Rubin 1987](#)).

With regard to multiplicity caused by the 2 primary endpoints, Holm's method ([Holm 1979](#)) will be utilized. First, an endpoint with a smaller p-value will be tested at alpha=0.025 (two-sided). If the first test is significant, another endpoint will be tested at alpha=0.05 (two-sided). Otherwise, the second test will not be performed.

Planned analyses at Day 85 including the primary analyses will be performed by unmasked team not involved in the conduct of the study once all patient data until Day 85 are obtained in a fashion to protect the masking of the patients who will be followed in extension. Masked team will have access only to a summary of the results comparing the two arms so the same study team can continue to be masked while conducting the remaining part of the trial until the end of the 52-week Overall Period. The investigational sites will not be unmasked and will not have access to the summary of the results comparing the two arms.

As a sensitivity analysis, a tipping point, at which the primary analysis result turns out to be not-significant, is examined in each ICE.

Further details will be included in a separated statistical analysis plan.

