Vehicle Run-In Dispensation	X										
Vehicle Run-In Instillation	X										
Vehicle Run-in Collection and Accountability		X									
Determination/assignment of the study eye		X									
Randomization		X									
Study Drug Dispensation		X				X ^d	X ^d	X ^d			
Study Drug Instillation		X		X	X	X ^d	X ^d	X ^d			
Study Drug Collection and Accountability				X ^e	X ^e	X	X ^d	X ^d	X ^d		
Fluorescein Staining Scoring	X	X		X	X	X	X	X	X		
VAS	X	X		X	X	X	X	X	X		
TFBUT	X	X		X	X	X	X	X	X		
Schirmer's Test	X	X		X	X	X	X	X	X		

ASSESSMENTS PERFORMED	STUDY PERIOD										Post-dose Assessments	
	Screening /Run-in Period	Days of Dosing and Assessments										
		52-week Overall Period										
		12-week Primary Period					40-week Extension Period					
Visit 1 Day -14 (Day -21 to -12)	Visit 2 Day 1 (Baseline)	Visit 3 Day 15 ± 2 (Remote) ^a	Visit 4 Day 29 ± 2	Visit 5 Day 57 ± 7	Visit 6 Day 85 ± 7	Visit 7 ^b Day 169 ± 7	Visit 8 ^b Day 253 ± 7	Visit 9 ^b Day 365 ± 7	Visit 6.5 ^b Day 99 ± 7 ^c or Visit 10 ^b Day 379 ± 7 ^c			
Adverse Event Collection	X	X	X	X	X	X	X	X	X	X		
Systemic Clinical Evaluation		X				X			X			
Clinical Laboratory Measurement	X					X			X			
Exit Patient from Study										X		

HIPAA=Health Insurance

Portability and Accountability Act; OSDI=Ocular Surface Disease Index; TFBUT=tear film break-up time; VAS=Visual analog scale.

Note: The visit schedule will always be calculated from randomization visit date (Visit 2).

- a. Visit 3 will be a remote visit.
- b. Only first 120 patients of each arm, approximate total 240 patients, will proceed to Visit 7 (Day 169) and following visits. Other patients will proceed to Visit 6.5 (Day 99) for post-dose assessments.
- c. Post-dose assessments will be performed at least 14 days after the last dose of study medication.
- d. Only patients in the Extension Period will be dispensed and instilled with the study drugs and will be examined for [REDACTED]

e. Patients will be instructed to bring all [REDACTED] to assess dosing compliance, however, only the used [REDACTED] will be collected and the [REDACTED] will be returned to patients at Visit 4 and Visit 5.

f. [REDACTED]

g. [REDACTED]

h. [REDACTED]

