9. TFBUT

10. Corneal and conjunctival fluorescein staining scoring

[REDACTED]

[REDACTED]

12. Schirmer's test (without anesthesia)

[REDACTED]

[REDACTED]

[REDACTED]

16. Clinical laboratory sample collection

17. Dispensation of study drug (run-in drops) for [REDACTED] dosing until the day before Visit 2

19. Patient instructions dispensation

20. AE collection

21. Patients will be scheduled for Visit 2.

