5.2 Efficacy Evaluations

Primary and secondary efficacy endpoints are specified in the Sections 2.2.1, 2.2.2, and 2.2.3.

Worst Eye (study eye): Eyes are eligible for analysis if they meet all of the inclusion criteria and do not meet any of the exclusion criteria. At least one eye (the right eye or the left eye) must meet all of the inclusion criteria and neither eye must meet any of the exclusion criteria. In the case that both eyes are eligible for analysis, the worst eye will be selected. The worst eye will be defined as the eye with the worst conjunctival sum staining score at Visit 2. If the staining score is the same in both eyes, then the right eye will be selected as the study eye. The contralateral eye will be defined as fellow eye.

[figure not shown]
5.2.1

[figure not shown]
[figure not shown]

5.2.2

[figure not shown]
Figure 2

[figure not shown]

5.2.3

5.2.4 [REDACTED]

A high-contrast, black and white image. The left side is a large, solid black rectangle. To its right is a white rectangle. Within the white rectangle, there is a small, dark, stepped or jagged shape, possibly a logo or a stylized letter. The overall image is grainy and has a high-contrast, almost binary appearance.

5.2.7 [REDACTED]

5.2.8 [REDACTED]

5.2.9 [REDACTED]

5.2.10 [REDACTED]

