6.0 CONDUCT OF STUDY

6.1 Study Masking and Randomization

All arms will be double-masked. The run-in drops will be single-masked for patients.

Before the initiation of study run-in at Visit 1, each patient who provides written informed consent will be assigned a subject code. All subject codes will be assigned in strict numerical sequence at a site and no numbers will be skipped or omitted. If a patient is retested on clinical labs, the same subject code will be used (Section 4.5.3). If a patient is rescreened, the patient will be assigned with a new subject code (Section 4.5.2).

Patients who have signed informed consent and subsequently fail to satisfy inclusion and exclusion criteria are defined as screen failures. For all screen failures, the reason(s) for screen failure will be recorded on the patient's source document and eCRF.

Each patient who meets all the inclusion and none of the exclusion criteria at Visit 1 and Visit 2 will be randomized at the end of Visit 2 by using the IWRS.

Subject codes and kit numbers will be assigned automatically to each patient as they are entered into the IWRS. All patients will be randomized into either vehicle or active treatment group at Visit 2 (Day 1) in a 1:1 ratio. [REDACTED]

[REDACTED] The first approximately 240 (120/arm) randomized patients will be assigned into the 52-week Overall Period and the rest of study population (approximately 380 [190/arm] patients) will be assigned into the 12-week Primary Period.

The site staff will dispense the required kit(s). Both the subject codes and the dispensed study drug kit number(s) will be recorded on the patient's source document and eCRF. Patients, sponsor, CRO, and site personnel will be masked to treatment assignment.

After Visit 6 (Day 85), patients who are randomized to enter the 40-week Extension Period will proceed to Visit 7 (Day 169) until Visit 10 (Day 379). Other patients, who are randomized to enter the 12-week Primary Period only, will proceed to Visit 6.5 (Day 99) for post-dose assessments and will complete the study.

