10.7 Demographic/Baseline Information

Summary statistics will be provided by treatment group for demographics (e.g., age, sex, race, ethnicity, eye color groups, and the prior use of [REDACTED]).

The baseline for all efficacy and safety variables will be Visit 2 (Day 1), while the baseline for clinical laboratory measurements and [REDACTED] will be Visit 1 (Screening Visit).

Further details will be included in a separated statistical analysis plan.

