Compliance will be considered as missing if the numerator or denominator in SAS Section 7.7.2 is not calculated due to missing data.

7. Statistical approach for primary efficacy endpoints

Originally, two statistical approaches were planned, namely multiple imputation (as outlined in SAP Section 8.1.2) and control-based mean imputation (as described in SAP Section 8.1.4). The former approach was planned to switch the latter one if there were not enough patients to develop imputation models. The decision to use the latter approach for the primary analyses was made based on the results of the data review meeting, which determined the final approach: control-based mean imputation.

8. Typo in the SAS code

From the formula in SAP Section 8.1.4:

$$\hat{V}(\hat{\delta}_{new}[c]) = \left[A_2 + (f_2^{k=1})^2 \right] (\hat{V}_2^{k=1} + \hat{V}_{1,MAR}) + \left[A_2 (\hat{\mu}_2^{k=1} - \hat{\mu}_{1,MAR} - c)^2 \right],$$

the sign is modified from "+" to "-" in the code in SAP Section 8.1.4 as follows:

```
V_delta_new_c= (A2 + (f2_k1)**2)*(V2_k1 + V1_MAR) + (A2*(mu2_k1 - mu1_MAR - c)**2);
```

Final programs have been corrected to reflect this.

9. Range of conservative values (c) for sensitivity analysis in SAP Section 8.1.6

The following ranges of c will be defined to find the tipping point c_t :

- Eye dryness score (visual analog scale): 0 to $(100 - \hat{\mu}_{1,MAR})$,
- Conjunctival sum fluorescein staining score: 0 to $(24 - \hat{\mu}_{1,MAR})$.

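### The primary ANCOVA omits the Visit 1 reading of each primary endpoint, although it is scheduled before randomization for every patient; adding it would probably gain precision at almost no cost.

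*Protocol*

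**What the plan says.** - **Model.** Protocol Section 10.4: "For each of the primary endpoints, the analysis of covariance with baseline value, sex and treatment as covariates is used". The synopsis gives the same covariates. Section 10.7 takes Visit 2 (Day 1) as baseline for all efficacy variables.
- **Visit 1 data.** Section 5.1.1.1 requires the screening assessments of all patients. They include the VAS as step 5 and, later in the list, "10. Corneal and conjunctival fluorescein staining scoring". Table 1 marks VAS and "Fluorescein Staining Scoring" at both Visit 1 and Visit 2.
- **Timing.** Under Section 6.1, eligible patients "will be randomized at the end of Visit 2 by using the IWRS". Both readings therefore precede randomization. Patients use vehicle drops for about 14 days between the two visits (Section 3.1).
- **Study eye.** Section 5.2, for patients with both eyes eligible: "The worst eye will be defined as the eye with the worst conjunctival sum staining score at Visit 2".
- **Sample size.** Section 10.1 assumes mean EDS changes of -10.0 (K-161, no intercurrent event) and -3.6 (all other patterns). It adds: "A common variance, 431.2, and a common ICE occurrence rate, 8%, are assumed among the patterns". It does not say whether that variance is before or after adjustment for baseline.
- **SAP addendum.** Item 7 refers to the data review meeting, "which determined the final approach: control-based mean imputation". No item of the addendum changes a covariate.

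**The concern.** A single VAS or staining reading is a noisy measure of a patient's underlying level. Two readings before randomization usually locate that level better than one, and so predict Day 85 better. The trial collects both and the stated model uses one. Treatment cannot affect a pre-randomization covariate, so adding it to a linear model leaves the estimand (difference in mean change from Visit 2 to Day 85) unchanged and can only help or do almost nothing.

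Precision matters on both primary endpoints. Under Holm's procedure the second is tested only if the first succeeds, and the key secondary endpoint only if both are significant. Section 10.1 justifies power for EDS alone; staining has no stated variance, effect or power.

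**Working it through.** **1. Reproduce the plan's figure.** Inputs from Section 10.1: means -10.0 and -3.6, intercurrent event rate 8%, variance 431.2, two-sided alpha 0.025, 310 per arm.

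- Difference = 0.92 × (-10.0) + 0.08 × (-3.6) - (-3.6) = -5.888.
- Power = Φ(5.888 / √(2 × 431.2 / 310) - 2.2414) = 90.1%.
- The sample size for 90% power is 309 per arm. It is exactly 310 (power 90.0%) if the spread between patterns in the active arm, 0.92 × 0.08 × 6.4², is averaged over the arms and added to the variance.

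The plan's figure holds.

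**2. Variance reduction from adding Visit 1.** Let r1 = correlation of Visit 1 with Day 85, r2 = Visit 2 with Day 85, r12 = Visit 1 with Visit 2. The proportional cut in residual variance is the squared partial correlation:

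cut = (r1 - r2·r12)² / [(1 - r2²)(1 - r12²)]

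With all three equal to ρ this is ρ²/(1 + ρ)². For (0.4, 0.5, 0.5): (0.4 - 0.25)² / (0.75 × 0.75) = 0.0225 / 0.5625 = 4.0%. The cut is zero only when r1 = r2·r12, that is, when Visit 1 relates to Day 85 solely through the observed Visit 2 score.

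**3. Effect on EDS power.** The documents give no correlations, so every row is an assumption.

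- Reading A: 431.2 is the residual variance after Visit 2 adjustment, so V = 431.2 × (1 - cut). Patients per arm saved = 310 × cut.
- Reading B: 431.2 is the variance of raw change, with equal variances across visits. The residual variance with Visit 2 alone is then 431.2 × (1 + r2)/2, which is 280.3, 323.4 or 366.5 for r2 = 0.3, 0.5 or 0.7. This is multiplied by (1 - cut).

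| (r1, r2, r12) | Variance cut | A: power (90.1% without Visit 1) | A: patients per arm | B: power without → with Visit 1 |
|---|---|---|---|---|
| (0.3, 0.5, 0.6) | 0% | 90.1% | 0 | 96.7% → 96.7% |
| (0.4, 0.5, 0.7) | 0.65% | 90.3% | 2 | 96.7% → 96.8% |
| (0.4, 0.5, 0.6) | 2.1% | 90.8% | 6 | 96.7% → 97.0% |
| (0.4, 0.5, 0.5) | 4.0% | 91.3% | 12 | 96.7% → about 97.2% |
| all 0.3 | 5.3% | 91.7% | 17 | 98.4% → 98.8% |
| all 0.5 | 11.1% | 93.4% | 34 | 96.7% → 98.1% |
| all 0.7 | 17.0% | 94.9% | 53 | 94.4% → 97.5% |

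**4. Selection effects.** Choosing the eye with the worse Visit 2 score uses part of the Visit 2 noise. In a simulation of 1,000,000 patients with within-eye correlations of 0.3, 0.5 and 0.7, the cuts were 5.0%, 10.3% and 15.9% with a between-eye correlation of true scores of 0.6. With 0.8 they were 4.8%, 9.5% and 14.7%. Separately, truncating both visits at illustrative entry thresholds, with equal underlying correlations of 0.5 to 0.7, left cuts of about 5% to 14%. Neither form of selection removes the gain.

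**5. Cost if Visit 1 adds nothing.** The planned model leaves 620 - 4 = 616 residual degrees of freedom, and one more covariate takes one of them. The variance penalty is about 615/614 - 1 = 0.16%.

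**The case against.** The strongest reply is that nothing is wrong: the model is valid, prespecified and adequately powered, and the benefit is entirely assumed, with a range that starts at zero. The larger figures need Visit 1 to predict Day 85 as well as Visit 2 does. The design makes that doubtful, because Visit 1 comes before the vehicle run-in and is further from Day 85. With modest decay the cut is 0.65% to 2.1%. Section 10.1 mentions no covariate adjustment, so Reading B is at least as natural as A, and under B the same cases move power by 0.3 points or less. All of this stands as a limit on size. It does not make the change harmful, since the worst case is a 0.16% penalty.

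Two further points have some force. First, cost: editing Section 10.4 is a protocol amendment under Section 11.4, and the October 2023 addendum describes blinded data review and program corrections already made. The new term would change the means feeding the control-based imputation and the tipping-point ranges in addendum item 9. That is real but limited work. Second, Section 10.4 leaves further detail to the SAP, and the main SAP, which may already include Visit 1, could not be checked. The claim is therefore confined to the protocol.

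**Conclusion.** The point holds as a recommended improvement and not as a correction. The facts are plain: a second pre-randomization reading of both primary outcomes is scheduled for every patient, and the protocol's primary model does not use it. A gain is likely, because single readings of symptoms and staining are noisy, but it is not established.

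Over the correlations tried, residual variance falls by 0% to 17.0%. For EDS this takes power from 90.1% to between 90.1% and 94.9% if 431.2 is a residual variance. If it is the variance of raw change, the gain runs from nothing to about 3 points, on power that already exceeds 94%. For staining no power can be computed. Confidence is moderate: the size rests on assumed correlations and on the unstated meaning of 431.2.

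**What to change.** Before unmasking, amend Section 10.4 and the matching SAP section as follows:

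- Add the Visit 1 value of the same endpoint as a second continuous covariate, using the same study eye for eye-specific scores. Keep Visit 2 as the baseline for change.
- Use the same model for the least squares means that enter the control-based mean imputation and its tipping-point analysis.
- Apply it to the secondary endpoints measured at Visit 1: total and corneal staining, Schirmer's test and TFBUT. Include OSDI only if it is collected at that visit.
- For rescreened patients, take Visit 1 from the screening that led to randomization. State in advance how a missing Visit 1 value is handled.
- If the main SAP already includes this covariate, align the protocol wording with it.

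The cost is one model term, one degree of freedom, a short text change through the amendment route, and re-running and checking the affected programs. No new data or patients are needed. If unmasking has already taken place, the model with both visits should be reported only as a supportive analysis.
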